## 7. Study Intervention(s) being tested or evaluated

*This can include prevention, diagnostic or therapeutic interventions (e.g., drug or device) or educational, health services or basic science interventions (e.g., educational program, health care delivery model, or examining basic physiology)*

**Cognitive Adaptation Training (CAT) (completed at baseline and once weekly for 6 months or until study completion; when allowable).**

Individuals choosing or assigned to CAT will continue to see all their current treatment providers and have CAT as an added service. CAT is a manual-driven, evidence based psychosocial treatment developed to bypass impairments in controlled

processes such as directed attention, problem solving, memory and motivation which often characterize individuals with SMI. CAT uses environmental supports such as signs, calendars, alarms, pill containers, and checklists to cue and sequence adaptive behaviors such as taking medication, socializing with others, and taking care of independent living skills. CAT environmental supports are established and maintained on weekly home visits. CAT has been disseminated to multiple countries and is a billable service for many community mental health centers in the U.S.

**R-CAT (completed at baseline and once weekly for 6 months or until study completion).**

Individuals choosing or assigned to R-CAT will continue treatment as usual with their health care team and R-CAT will be added. R-CAT is a remotely delivered version of CAT focused on medication adherence using a series of manual-driven compensatory strategies and environmental supports (signs, checklists, electronic cueing devices) based upon a streamlined assessment of executive function impairment and barriers to habit formation including forgetfulness, difficulties in problem-solving, disorganization, apathy or amotivation, disinhibition, and home environment. Initial R-CAT goals are to 1) ensure that medications listed as prescribed are available 2) to assess current cognitive, behavioral and environmental facilitators and barriers to habit-formation 3) to set up customized CAT supports to address the barriers and use facilitators to build habits to take medication. Rare home visits may occur if issues cannot be resolved remotely. Based upon the pilot, we don't anticipate any more than 5-10% of individuals to need face-to-face visits. No one had home visits as part of our pilot intervention. A structured R-CAT treatment note with places for pictures of CAT interventions is used for home visits. Support and reminder calls use a brief checklist modified from the Healthy Habits Program to address issues in use of supports, placement of supports and habit formation. Examples of CAT interventions to promote taking medication regularly appear above. All home visits and phone calls will be audio-taped (with consent) for quality assurance.

**8. Protocol-Directed procedures, items, services or tests**

*List all procedures directed by the study plan - including items or services provided as part of routine or conventional care and those needed to diagnosis or treat research related complications.*

**Important Note – The protocol directed procedures listed must match those in the Schedule of Activities (attachment)**

**8.1. Drugs (trade and generic, dosage, route of administration)**

**8.2. Devices**

**8.3. Biologics**

**8.4. Laboratory Tests**

**8.5. Imaging Procedures**

**8.6. Other Research Procedures (e.g., other safety and efficacy assessments.)**

**Part 1:**

Telephone interviews: based upon a list provided by Superior Medicaid as possibly meeting inclusion criteria for the pilot study, the research team will call individuals to invite them to participate in a telephone interview. Verbal consent will be obtained from those interested in participating, and the interviews will be recorded over the phone. The interview will involve the researcher describing the R-CAT and CAT programs and after a description of each, participants will be asked a series of questions to assess their attitudes and acceptance of each program. Those who complete the telephone interview will be informed about the clinical trial (Part 2) and will undergo a general screening (described below) if interested.

**Part 2:**

**Telephone Pre-screening (screening visit)** - based upon a list from superior Medicaid we will call individuals to determine whether they meet inclusion criteria outlined above and ask them about their interest in participating. **Diagnosis.** Will be based upon the clinical diagnosis (DSM-5) of the treating prescriber. This is done to improve ease of implementation in health maintenance organizations.

**Acceptability/Feasibility (ongoing)** - will be based upon numbers of individuals accepting initial offers of CAT or R-CAT, numbers with and without preferences for either treatment, and reasons for choosing / not choosing one add on treatment versus another. In addition, we will examine drop-out rates by treatment group and reasons for drop out. Barriers and facilitators to the selected or assigned treatment and treatment satisfaction will be queried at routine assessments.

**Symptomatology (baseline and at Months 2, 4 and 6)** - Symptoms will be assessed by a trained rater using the Brief Psychiatric Rating Scale-Expanded version. A total score reflects an overall level of symptomatology. (20 minutes).

**Medication Adherence (baseline and once monthly until 6 months or study completion)** - based upon our own work and recent publications, medication adherence will be assessed using unannounced in-home pill counts conducted every other month (months 0, 2, 4, 6) with video counts done in the intervening months (1, 3, 5). We will also have electronic claims data provided by the MCO. The primary measure will be in-home pill counts due to evidence that this measure is more sensitive to treatment changes. An initial visit prior to randomization [or initiation of chosen intervention] is conducted to count and bag all old pills, identify current bottles, count current pills in the bottles and any medication containers used by the individual. A box is set up with a sign to remind participants not to throw out empty bottles. Counts are conducted monthly in an attempt to capture all prescription refills and medication changes. Adherence percent is calculated as the number of pills missing and presumed taken/ the number of pills prescribed for the time period X100. Percentage of all mental health medications and a percentage for all medications will be calculated. The latter being the primary measure. We used these procedures in two R01's previously. We will also obtain prescription refill data from MCO records. We will calculate Medication Possession Ratio (MPR) and Proportion of Days Covered (PDC) as secondary measures of adherence. MPR is calculated as the day's supply for all fills of a medication in the time period divided by the number of days in the time period X 100. PDC is calculated by the number of days "covered" divided by the number of days in the time period X 100. PDC is less commonly used but is endorsed by the Pharmacy Quality Alliance and is now incorporated into Medicaid and Medicare services in their plan ratings. Moreover, for individuals on multiple medications, PDC better characterizes overall adherence. (20-40 minutes depending upon person's organization and number of medications).

**Automaticity (Habit Strength) (baseline and at Months 2, 4 and 6)** - the Self-Report Habit Index (SRHI) 68 is a 12-item scale assessing three proposed characteristics of habit;1) automaticity (e.g., I take medication without thinking), 2) frequency ('... I take medication frequently), and 3) relevance to self-identity ('taking medication is a behavior that's typically "me"'). The SRHI has good reliability and convergent, discriminant, and predictive validity as a measure of habit. Four items of this scale, items 2,3,5 and 8 represent the Self-Reported Behavioral Automaticity Index (SRBAI). This index is based upon research suggesting that automaticity also called habit strength is the active ingredient in habit. The SRBAI has been found across studies to be related to habit and to predict future behavior. Lower scores indicate greater habit strength and greater automaticity. A mean Habit score will be computed using the entire scale. Automaticity (SRBAI score) will be the primary measure used to examine the paths among the target behavior (adherence) and habit strength. The mean SRHI will be used in secondary analyses. (10 minutes)

**Functional Outcome (baseline and at Months 2, 4 and 6)** - Functional outcome will be rated using the Social and Occupational Functioning Scale (SOFAS). The SOFAS rates functioning on a scale from 0 to 100 based upon all the data collected in the assessment. Higher scores reflect better functional outcome. Symptoms are not taken into account in the rating. (0 minutes).

Remote monitoring/remote visits will occur using UTHSCSA licensed Zoom. Audio-recording of remote visits will be conducted through the Zoom platform with participant consent. Therefore, privacy and confidentiality is not guaranteed due to the nature of the electronic conferencing platforms that will be used.

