### 12.2. Sample Size Determination

Include number of participants to recruit, screen, and enroll to have adequate power to test the key hypotheses for the study. Provide all information needed to validate your calculations and judge the feasibility of enrolling and following the necessary number of participants.

This is a pilot study and not powered for testing efficacy. Given that, we examined power for proportions using PASS (Aims 1 and 2). We will approach a minimum of 200 individuals to examine the acceptance rates of an initial offer of CAT versus R-CAT. We will be able to detect a 20% difference in proportions in acceptance with a power greater than .80; two-tailed alpha =0.05. We don't expect dropout rates to vary greatly between the 2 treatments but with 100 individuals and 50 in each of 2 treatment groups we will be able to detect a difference in drop out of at least 10% versus 30% at a power of .80; alpha=0.05. A smaller difference in dropout across 6 months would not be likely to impact decisions about which treatment to adopt and is not important to detect. Aim 3 examines differences from baseline within 4 groups (those with a preference for CAT; those with a preference for R-RCAT; those with no preference randomized to CAT and those with no preference randomized to R-CAT). With 25 per group for the randomized samples within each treatment SAS Power indicates that the smallest detectable effect would be for pill count adherence going from 70% to 85%. We would have power of .80 to detect difference of about 25% in pill count adherence proportions that that correlate .48 with probabilities of adherence from 60-85% in with a one tailed test at alpha of .05. <http://statulator.com/SampleSize/ss2PP.html>. This was verified using a simulation using 5000 replications. A one-tailed test is used as we are not interested in whether the intervention makes adherence worse.

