#### **Aim 3**

The primary variable is in-home pill count percent established on each monthly visits or virtual visits. Secondary variables are MPR, PDC, SRHI automaticity SRHI total score, Symptoms and SOFAS scores. We will examine within group change and effect sizes using a likelihood-based population-averaged (marginal) generalized linear regression model with repeated measures as implemented in the SAS GLIMMIX procedure specifying binomial (proportions) or normal (scales) as appropriate. A-likelihood based regression model with repeated measures makes the best use if all the information including cases with incomplete or missing data. The primary hypothesis tests planned contrasts at the final assessment of within-arm change and the difference between arms.

We will examine trajectories for 4 groups; the 2 groups with a preference (for either R-CAT or CAT) that were self-selected the 2 groups who did not indicated a preference and were randomized to either CAT or R-CAT. We will examine differences in baseline characteristics between the two groups with preferences as these differences may be related to outcome in the self-selected samples.

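### The primary pill-count percent has no per-drug limit, so pills of one drug missing beyond the number prescribed can offset missed doses of another

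*Combined protocol and SAP*

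**What the plan says.** Section 8.6 (Part 2, Medication Adherence) gives the formula: "Adherence percent is calculated as the number of pills missing and presumed taken/ the number of pills prescribed for the time period X100". On several drugs it says: "Percentage of all mental health medications and a percentage for all medications will be calculated. The latter being the primary measure". Section 12.4 (Aim 3) confirms the status of the measure: "The primary variable is in-home pill count percent established on each monthly visits or virtual visits". The model there is a repeated-measures generalized linear model, "specifying binomial (proportions) or normal (scales) as appropriate".

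Section 8.6 sets no upper limit for a drug or for the total. It does not say what to do when a count exceeds the number prescribed, or whether drugs are pooled or their percents averaged. Sections 12.2, 12.3 and 12.4 add no truncation rule.

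The plan does describe how counts are kept complete. Before treatment begins, staff "count and bag all old pills, identify current bottles, count current pills in the bottles and any medication containers used by the individual". A box for empty bottles is set up, and counts are monthly, in the home at months 0, 2, 4 and 6 and by video at months 1, 3 and 5. The plan expects members on several drugs and says of a secondary, refill-based measure: "Moreover, for individuals on multiple medications, PDC better characterizes overall adherence".

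**The concern.** The quantity intended is evidently the share of prescribed doses that the member took. For any one drug that share cannot exceed 100%. The formula places no such limit on the numerator, which has two consequences.

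- Excess on one drug is credited against a shortfall on another, so a member who missed many doses of one drug can score as fully adherent.
- The score itself can pass 100%. It is then no longer a proportion, and a binomial model does not admit more successes than trials.

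Section 3 lists pill count percent as the primary efficacy endpoint of Aim 3 and says that the results are to inform future trials. A score that reads over-use or unexplained loss as better adherence would carry into those estimates.

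**Working it through.** **Inputs.** The formula and the choice of primary measure are from section 8.6; the model is from section 12.4. The plan states no figure for this point, so there is none to reproduce. The regimens below are illustrations, not trial data.

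**Formulas.** For drug j in one interval, let p be the pills prescribed and m the pills missing and presumed taken.

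- As written, pooled: U = 100 × Σm / Σp
- As written, averaged over drugs: A = mean of 100 × m/p
- Limited per drug, then pooled: L = 100 × Σ min(m, p) / Σp
- Inflation under pooling: U − L = 100 × Σ max(m − p, 0) / Σp

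**Results.**

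| Prescribed | Missing | U | A | U with a limit on the total only | L |
|---|---|---|---|---|---|
| 30, 30 | 33, 27 | 60/60 = 100% | (110+90)/2 = 100% | 100% | 57/60 = 95% |
| 30, 30 | 42, 18 | 60/60 = 100% | (140+60)/2 = 100% | 100% | 48/60 = 80% |
| 30, 30 | 45, 15 | 60/60 = 100% | (150+50)/2 = 100% | 100% | 45/60 = 75% |
| 60, 30, 30, 30 | 75, 15, 30, 30 | 150/150 = 100% | (125+50+100+100)/4 = 93.8% | 100% | 135/150 = 90% |
| 30 | 36 | 36/30 = 120% | 120% | 100% | 30/30 = 100% |
| 30, 30 | 45, 30 | 75/60 = 125% | (150+100)/2 = 125% | 100% | 60/60 = 100% |
| 30, 30 | 30, 18 | 48/60 = 80% | 80% | 80% | 80% |

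The offset occurs under pooling and under averaging, though its size under averaging depends on the regimen. In the four-drug row the averaged score with a per-drug limit is (100+50+100+100)/4 = 87.5%, against 93.8% without. A limit on the total alone leaves the first four rows at 100%. With no excess on any drug (last row) nothing changes.

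**Effect on the contrasts.** Since U = L + E, where E is the inflation above, the mean within-arm change in U equals the change in L plus (mean E at the final assessment − mean E at baseline). The between-arm difference is shifted by the difference in mean E between arms. On the percentage scale both shifts are zero if E is the same at both times or in both arms.

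**What the limit does not remove.** A simulation used two drugs of 30 pills, each dose taken with probability 0.7 (true adherence 70.0%), and an assumed chance per drug that a further 5 to 15 pills are missing and presumed taken.

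| Assumed chance per drug | Mean U | Mean L | U − L | Members above 100% |
|---|---|---|---|---|
| 10% | 73.3% | 72.6% | 0.7 | 1.2% |
| 20% | 76.7% | 75.2% | 1.5 | 3.5% |
| 30% | 80.0% | 77.8% | 2.2 | 6.8% |

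The limit removes only the credit above the prescribed number. Lost pills that leave a drug at or below that number still count as taken. These chances are assumptions and do not estimate what will happen in the trial.

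**Downside of the limit.** Take one drug of 30 pills per interval, all taken, with 3 pills overlooked at a video count and found at the next home visit. The counts are 33 and 27. Without the limit the two intervals together give 60/60 = 100%, which is correct; with it they give 57/60 = 95%.

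**The case against.** Several points on the other side stand.

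- The formula does not credit every missing pill. A pill must also be presumed taken, so a counter who knows that pills were lost, discarded or moved may leave them out. But no rule for doing so is written, and the words do not exclude doses taken in excess.
- Bagging old pills, counting containers, keeping empty bottles and counting monthly all work against spurious excess. They bear on how often it arises, not on the credit given when it does.
- Section 8.6 says the procedures were used in two earlier grants, so a handling rule may exist in operating documents. If it does, it should be written here.
- The study is a pilot, and MPR, PDC and a mental-health-only percent are also calculated. The first two are refill-based and the third uses the same formula, so none repairs the primary score.
- A limit has its own bias, as the 33 and 27 example shows.

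Two stronger readings are tempting and are not supported. A reader might set one member's inflation beside the effect in section 12.2 ("We would have power of .80 to detect difference of about 25% in pill count adherence proportions"). That figure is a group-level difference and cannot be compared with one person's score. A reader might also infer that the arms will differ, because CAT staff work in the home weekly while R-CAT is mainly remote. Nothing in the documents shows that home work creates excess missing pills. It could as well reduce it, and section 10.1 keeps pill counters unaware of treatment group.

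**Conclusion.** The point holds as a defect in how the primary score is defined. Taken literally, the formula lets excess on one drug offset missed doses of another and allows scores above 100%. For an individual, the inflation under pooling is the excess pills divided by all pills prescribed: 5, 20 and 25 points in the first three examples.

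The conclusion rests on two conditions: at least one drug has more pills missing than prescribed in an interval, and the excess is presumed taken. The documents do not say how often this happens, so no trial-level bias can be stated. Bias in the within-arm or between-arm contrasts needs an excess that differs over time or between arms, which the documents neither show nor rule out. No sample-size figure is affected.

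**What to change.** In section 8.6, state that the pills counted as taken for each drug in each interval are limited to the number prescribed for that drug in that interval, and that this is done before drugs are combined into the all-medications and mental-health percents. State also whether drugs are pooled or averaged. Record the excess separately by drug and interval, so that its frequency can be reported by time and arm. Report the uncapped score as a sensitivity analysis. That analysis would also preserve comparability with historical CAT data, should the comparison allowed for in section 4 be made.

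The cost is one or two sentences in the protocol and one line in the derivation. The separate mental-health percent already requires drugs to be identified, so counts by drug should be available. The small downside is that a count error between adjacent home and video intervals no longer cancels and can bias the capped score slightly downward. The uncapped analysis would show this.

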## 6. Study Population

6.1. Study Population(s) Label/Name  To add more populations – select a row, copy & paste	6.2. Identify the criteria for inclusion The criteria that every potential participant must satisfy, to qualify for study entry.  All individuals in this study population must meet all of the inclusion criteria in order to be eligible to participate in the study	6.3. Identify the criteria for exclusion The characteristics that make an individual ineligible for study participation.  All individuals in this study population meeting any of the exclusion criteria at baseline will be excluded from study participation.
Serious Mental illness (Major Depressive Disorder, Bipolar Disorder, Schizophrenia/Schizoaffective Disorder)	1. Able to give informed consent. 2. Between the ages of 18 and 65. 3. Clinical Diagnosis of Major Depressive Disorder, Bipolar disorder, Schizophrenia, or Schizoaffective Disorder 4. Receiving treatment with oral psychiatric medications. 5. Have had a hospitalization or emergency department visit in the past year 6. Have a Medication Possession Ratio (MPR) based upon electronic refill data below 80% at least 1 of the past 4 quarters with at least 1 psychiatric medication 7. Responsible for taking their own medications 8. Report on telephone prescreen call with researcher team that they have missed at least 2 doses of medication in the past 3 weeks, that they are willing to take medication and would like remote assistance to take medication more regularly 9. Report on telephone prescreen call with research team that they have a stable living environment (individual apartment, family home, board and care facility) within the last three months and no plans to move in the next year 10. Report on prescreen research call with research team that they have no plans to change their MCO in the next 12 months 11. Have a working smart phone 12. Able to understand and complete rating scales and assessments. 13. Agree to home visits for intervention and to count pills and conduct assessments	1. Substance dependence within the past 2 months 2. Currently being treated by an ACT team 3. Documented history of violence or threatening behavior on initial assessment 4. Receive home visits to assist with medication adherence 5. Unable to complete baseline assessments

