### 10.3. Permitted Concomitant Therapy

This section should be consistent with the medication restrictions in the inclusion/exclusion criteria previously listed. Describe how allowed concomitant therapy might affect the outcome (e.g., drug-drug interaction, direct effects on the study endpoints).

All concomitant therapies are allowed during the study.

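### MPR divides each medication's supply by every day in the period, so a prescriber-ordered stop, start or switch scores as non-adherence; MPR and PDC also lack a rule for days after leaving the MCO

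*Combined protocol and SAP*

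**What the plan says.** Section 8.6, Part 2 (Medication Adherence) sets out three adherence measures.

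- **Pill count (primary).** Pills missing and presumed taken, divided by pills prescribed. Counts are monthly, partly so that refills and medication changes are captured.
- **MPR.** Days' "supply for all fills of a medication in the time period divided by the number of days in the time period", times 100.
- **PDC.** "PDC is calculated by the number of days 'covered' divided by the number of days in the time period X 100".

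The status of the last two is explicit: "We will calculate Medication Possession Ratio (MPR) and Proportion of Days Covered (PDC) as secondary measures of adherence". Their source is also given: "We will also obtain prescription refill data from MCO records". Section 3 lists MPR as an Aim 3 endpoint, and section 12.4 (Aim 3) names both MPR and PDC as secondary variables in the repeated-measures model.

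Neither section 8.6 nor section 12.4 defines the length of the time period, what makes a day covered, how MPRs for several drugs are combined, or what happens to the denominator when a drug is stopped, started or replaced or when a member leaves the MCO.

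Two other provisions bear on whether such events can arise. Section 10.3 states "All concomitant therapies are allowed during the study". Criterion 10 in section 6.2 asks members only to report that "they have no plans to change their MCO in the next 12 months".

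**The concern.** The primary measure and MPR respond differently to the same event. When a prescriber changes a drug, the pill-count denominator changes with it and the MPR denominator does not. A member who did everything asked can score 100% on the pill count and far lower on MPR. A reader would take that gap as a difference between taking and refilling, when it comes from the formula.

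Leaving the MCO raises a related problem. Fills are seen only in MCO records, so later fills are invisible. Unless the plan says those days are unobserved, they can be counted as days without supply.

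At stake is the reading of the claims-based outcomes. Section 12.4 plans contrasts of within-arm change and of the difference between arms at the final assessment. Two of its four groups are self-selected, so equal rates of drug changes or departures cannot be taken for granted.

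**Working it through.** The plan states no figure that depends on these definitions, so there is nothing to reproduce. The check applies the section 8.6 formulas as written to a member who refills perfectly.

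**Inputs**
- MPR and PDC formulas, pill-count denominator: section 8.6.
- Treatment length of 6 months: section 4. Taken here as one 180-day period (assumption; the plan does not define the period).
- Supply equal to the days on which the drug was prescribed (assumption).
- Event days and numbers of leavers (assumptions; the documents give none).

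**1. Prescriber-ordered switch on day 60, MPR**
- Old drug: 60/180 = 33.3%.
- New drug: 120/180 = 66.7%.
- In general, a switch on day t gives t/180 and (180 − t)/180, which always sum to 100%. If the two were averaged, the result would be 50% for any t. The plan does not say whether they are averaged.
- Pill count for the same member: pills taken equal pills prescribed for each drug, so 100%.
- With prescribed days as the denominator: 60/60 and 120/120, both 100%.

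**2. The same switch, PDC**
- If a day is covered when any drug is on hand: 180/180 = 100%, no loss.
- If PDC is computed per drug: 33.3% and 66.7%, as for MPR.
- The text does not settle which applies.

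**3. Leaving the MCO, later days kept in the denominator (MPR and PDC)**

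| Leaves after month | Calculation | Score |
|---|---|---|
| 1 | 30/180 | 16.7% |
| 2 | 60/180 | 33.3% |
| 3 | 90/180 | 50.0% |
| 4 | 120/180 | 66.7% |
| 5 | 150/180 | 83.3% |

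Over enrolled days only, every row is 100% (for example 120/120).

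**4. Illustrative effect on a group mean**
- Each perfectly refilling member who leaves on day 120 loses 100 − 66.7 = 33.3 points.
- If 5 of 50 in an arm leave then: 5/50 × 33.3 = 3.3 points.
- If 3 of 25 in a randomized group leave then: 3/25 × 33.3 = 4.0 points.

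**The case against.** The strongest reply is that much of this is ambiguity in a secondary measure. The period is undefined. Over shorter intervals, months after departure would simply have no claims data, and section 12.4 chooses a likelihood-based model partly to use incomplete cases. That stands for disenrolment: the 67% cap arises only if unobserved days are counted as days without supply, which the plan neither says nor rules out. It does not answer the MPR point, because there the plan states a rule, and the rule gives the wrong score for a changed prescription.

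A reader might infer four stronger claims that the documents do not support.

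- **That a switch lowers PDC as it lowers MPR.** Only the MPR sentence is written per medication. Section 8.6 says PDC better describes overall adherence for people on several drugs, which suggests a person-level measure.
- **That within-arm change is biased downward.** The formula applies before and after baseline. A drug change before baseline depresses the starting value and makes later MPR rise; one afterwards does the reverse. No net direction follows.
- **That drug changes and departures will be common.** Section 10.3 permits changes but gives no rate, and criterion 10 should reduce departures.
- **That criterion 6 wrongly admits members who were merely switched.** It reads "Have a Medication Possession Ratio (MPR) based upon electronic refill data below 80% at least 1 of the past 4 quarters". On an assumed 91-day quarter, a stop on day 72 gives 72/91 = 79.1%, but day 73 gives 73/91 = 80.2%, so not every stop qualifies. A switch can put one of the two drugs under the threshold, but all criteria must be met, and criterion 8 separately requires self-reported missed doses. Refill records alone also cannot separate a prescriber's stop from a patient who ceased refilling, so restricting criterion 6 to active drugs could exclude the intended population.

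**Conclusion.** The point holds for the outcome definitions. As written, MPR scores a prescriber-ordered stop, start or switch as non-adherence: 33% and 67% instead of 100% for a switch on day 60 of an assumed 180-day period with perfect refilling. For disenrolment the point is conditional: MPR and PDC are capped at 67% for departure on day 120 if the later days are retained. For PDC under a switch, the result turns on an undefined term.

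The group-mean figures of 3.3 and 4.0 points rest on assumed departures and only show scale. The primary pill count is unaffected, and section 12.2 describes a pilot not powered for efficacy. This is therefore a correction worth making to the secondary outcomes, with no bearing on the primary result and no change needed to criterion 6.

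**What to change.** In section 8.6, with a cross-reference from section 12.4:

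1. State the assessment period for the claims measures.
2. Define the MPR denominator, for each medication, as the days in that period on which the drug was prescribed, using changes captured at the monthly counts, and the member was enrolled in the MCO.
3. Define PDC at person level as covered days over enrolled days, state what makes a day covered, and count a prescriber-ordered replacement as continuous cover.
4. Treat claims outcomes after MCO disenrolment as missing, not as zero fills.
5. Report the all-days MPR as a sensitivity analysis.

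Leave criterion 6 as it is.

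**Cost.** A few sentences, plus enrolment dates in the MCO data pull. Medication changes are already recorded monthly during follow-up. The main drawback is that members who stop attending counts will lack change dates, so the revised MPR relies on visit data that the claims measure does not otherwise need; item 5 shows how much that matters. Setting post-departure values to missing also relies on the model's missing-data assumption, so the number of departures per group should be reported.
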